**Protocol**

**Proposal Summary**

This proposal aims to investigate the effect of a promising treatment for persistent post Traumatic Brain Injury (TBI) symptoms, and to monitor TBI patient's recovery by an objective technique along with standard clinical assessments. The treatment tool is the application of repetitive Transcranial Magnetic Stimulation (rTMS) [1] to the dorsolateral prefrontal cortex (DLPFC) of the brain. The treatment efficacy and monitoring TBI patients' recovery will be objectively assessed using Electrovestibulography (EVestG™) [2]; this will be in parallel with clinical and standard assessments. This proposal is built upon our encouraging pilot studies (*REB# B2011:116 and REB# B2012:076*)

TBI is a significant health problem mainly because of its plausible prolonged sequelae and lack of objective measures for recovery. The conventional treatment after a TBI is physical rehabilitation that helps with motor functional recovery. However, there are usually some disabling persistent post-TBI symptoms (mostly neurological) that do not respond to the current clinical and physical rehabilitation. rTMS, on the other hand, is a promising, well-tolerated, non-invasive brain neuromodulation technique that has emerged as a therapeutic tool for a variety of neurological conditions. Thus, we aim to investigate the effect of rTMS treatment on post-TBI symptoms in patients identified by our medical collaborators (Drs. [name] and [name]). Equally important is to have an objective measure of treatment efficacy and patient's symptoms recovery. EVestG™ [2] is a noninvasive technique to record neural activity from the vestibular apparatus and vestibular nuclei in the external ear. After a head injury, people commonly experience balance (vestibular) problems and dizziness, as well as confused thinking. Considering the well-known bidirectional anatomical links of the vestibular system, following an impact TBI, EVestG signals are expected to change, and our pilot studies show a great potential of EVestG to monitor the impact of TBI. Thus, we aim to use EVestG as an objective measure to monitor the recovery path during and after the rTMS treatment in parallel to clinical and neuro-psychological assessments.

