**ElectroVestibulography (EVestG)** – EVestG [1] is a noninvasive technique to record neural activity from the vestibular apparatus and vestibular nuclei. EVestG signals are recorded from the external ear in response to a vestibular stimulus. They are the brain signals modulated by the vestibular response. The recorded signal is comprised of a series of acoustic and vestibular random and driven generated small field potentials from which the vestibular response can be separated. The vestibular response can be separated by taking measures when the vestibular system is at rest and when perturbed by passive whole body tilt [52]. EVestG signal analysis has shown great promise for diagnosis and separation of patients with depression [53], Parkinson's disease [54], schizophrenia [55], Meniere's disease [56], Attention Deficit Hyperactivity Disorder [57] from healthy controls. Pilot studies have shown EVestG to have sensitivities and specificities above 85% for a population of between 40 and 50 years of age.

TBI is commonly associated with vestibular dysfunction, and many survivors often experience persistent dizziness, imbalance, vertigo [16, 17]. Considering the well-known bidirectional anatomical links of the vestibular system (i.e., the vestibular nucleus is linked to the pre-frontal cortex path), EVestG signals are expected to change following TBI, and should be indicative of an injury. A recent pilot study conducted by our group has demonstrated that evaluation of vestibular performance using EVestG might be a useful measure of the physiological recovery state following mTBI (see Figure 1) [58]. Hence, physiological EVestG assessment may offer a great promise in evaluating treatment efficacy and monitoring of recovery after TBI.

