### Theme 1: Applying rTMS treatment and its evaluation by neuropsychological and clinical assessments

1. Recruit people (from Riverview Health Center and also from [name] referrals), who have had a head injury within the past two to 12 months, have a clear diagnosis of TBI, and have persistent post-TBI symptoms. Collect standard neuropsychological assessment data at baseline.

2. Enroll the study participants into a “Sham Group” and a “Treatment Group” with a three-week protocol, and apply the treatment.
3. Record spatio-temporal assessments before and after treatment sessions, and examine the efficacy of rTMS treatment on the post-TBI symptoms by standard clinical and neuropsychological assessments by statistical analysis.

Theme 2: Monitoring treatment efficacy by objective measures, EVestG and spatio-temporal assessments

4. Record EVestG data with all its seven current stimuli at baseline (before the treatment) and immediately after treatment and also four and eight weeks after the last treatment.
5. Analyze EVestG data for extracting the optimum measures (biofeatures) showing the changes due to rTMS treatment.
6. Optimize (reduce the number of stimuli if possible) the EVestG recording protocol upon the results of Objective 5.
7. Examine the statistical correlation of the EVestG biofeatures representing the TBI recovery with data from the clinical and neuropsychological assessments as well as spatio-temporal assessments (derived in Objective 3).

Theme 3: Evaluating the objective measures of EVestG and spatio-temporal assessments in Control group

8. Recruit 20 age-and-gender-matched individuals with no history of head injury and record their EVestG data four times with a similar schedule to that of TBI patients, and investigate the consistency of the EVestG data between the sessions and compare with those of people with TBI during treatment.
9. Run the spatio-temporal assessments at the same sessions of EVestG recording in the Control Group and examine the effect of learning on the performance in these assessments.

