### **Study Protocol**

#### **Study Population/Participants**

A total of 20 individuals with a clear diagnosis of TBI within the last 12 months (as confirmed by their treating Neurologist, Psychiatrist or Medical Rehab Physiatrist, who are the co-investigators in this study) prior to the commencement of this study will be recruited from Riverview Health Center patient and [name] clinic patient population. Ten patients will be randomly assigned to **Treatment Group** and 10 others to **Sham Group**. Neither the patients, nor the clinical assessors will know the sham versus real treatment group assignment. In addition, as one of the objectives of this study is to evaluate the EVestG assessment as a

diagnostic and monitoring tool, 20 age-and-gender-matched cognitively healthy volunteers will be recruited as controls for the EVestG assessment. The healthy **Control Group**'s participants must not have any history of TBI and also meet other exclusion criteria for patients group listed below.

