### **Data analysis**

**EVestG Biofeature Extraction** – The NEER algorithm [52] will be used to locate and extract vestibular neural events. The interval histograms of the neural events are also used to extract the basic statistical properties of the neural firings such as probability density function (pdf), mean and variance, as well as fractal dimension, kurtosis and skewness of the signal. The features extracted from all tilts will be investigated to determine biofeatures specific to a concussion. The extracted biofeatures, e.g. fractal dimension, kurtosis and skewness of the potentials' distribution, from the recorded signal will be compared between Sham and Treatment Groups.

[figure not shown]
**Statistical Analysis, Clustering, Decision Making and Validation** – After data collection, the multivariate Analysis of Variance (MANOVA) statistical test will be run to determine the significant differences of any of the extracted biofeature measures between the sessions and the Control Group and the Treatment and Sham Groups. In all instances, a p-value less than 0.05 is considered significant. Cross correlation analysis will also be used to find the correlation between these measures and the neuropsychological assessments scores. Once the statistically significant features among the groups are found, the classic approach of discriminant analysis with leave-one-out routine (for robust results in small size data) will be run to investigate whether concussion cases can be identified. An important issue to address is the membership assignment of the subjects. Since there may not be confirmed and solid clinical and neuropsychological assessments for the recovery from the TBI post-symptoms, we will also run unsupervised (blind) clustering of the objective measures followed by our recently developed diagnostic decision making algorithm to identify TBI recovery. The diagnostic and monitoring algorithms will be checked with the updated diagnoses of the clinical symptoms (by the referring physician) and the neuropsychological evaluations.

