**Table 1: Treatment and Assessment Schedule**

Study Groups	Week	# of Treatments	Assessments
Treatment and Sham Groups	0 (Baseline)	None	EVestG, MoCA, MADRS, RPQ, Stroop, and spatiotemporal
	1	5 – Monday to Friday	None
	2	5 – Monday to Friday	None
	3	2 – Mon/Wed or Tue/Thu	None
	4		EVestG, MoCA, MADRS, RPQ, Stroop and spatiotemporal
	8		EVestG, MoCA, MADRS, RPQ, Stroop, and spatiotemporal
	12		EVestG, MoCA, MADRS, RPQ, Stroop, and spatiotemporal
Healthy Control Group	0		EVestG, MoCA, MADRS
	1		
	2		
	3		
	4		EVestG
	8		EVestG
	12		EVestG, MoCA, MADRS

**Figure 1.** Separation of mTBI and control subjects using two post potential features.

**Figure 2.** A) Sitting up/down movement, supine up/down movement, sitting horizontal rotation. B) Ear Electrode; C) Electrode placement; D) Subject connections.

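### The EVestG case in mTBI rests on a two-feature pilot separation, but the analysis plan does not pre-specify a test of those features; it selects features and estimates accuracy in the same subjects

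*Combined protocol and SAP*

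**What the plan says.** The Proposal Summary states: "This proposal is built upon our encouraging pilot studies". In the Background section on EVestG, the evidence specific to mild TBI is the group's pilot: "A recent pilot study conducted by our group has demonstrated that evaluation of vestibular performance using EVestG might be a useful measure". That sentence points to Figure 1, whose caption reads: "Separation of mTBI and control subjects using two post potential features". The same section gives a diagnostic figure, "Pilot studies have shown EVestG to have sensitivities and specificities above 85% for a population of between 40 and 50 years of age", but does not say that it concerns TBI.

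The Data analysis section does not carry the two features forward. It says: "The features extracted from all tilts will be investigated to determine biofeatures specific to a concussion". Features found significant by MANOVA at p below 0.05 then enter a discriminant analysis with leave-one-out. Unsupervised clustering, a recently developed decision algorithm and a check against updated clinical diagnoses follow. Objective 5 sets a further search: "Analyze EVestG data for extracting the optimum measures (biofeatures) showing the changes due to rTMS treatment".

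The recordings for a baseline test are already planned. Under Study Population/Participants the patients are "A total of 20 individuals with a clear diagnosis of TBI within the last 12 months", and for comparison "20 age-and-gender-matched cognitively healthy volunteers will be recruited as controls for the EVestG assessment". Under EVestG Measurement and in Table 1, all three groups are recorded at week 0, before any stimulation.

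**The concern.** When a study is justified by an earlier result, the most informative first use of new subjects is to apply that result to them unchanged. Such a test involves no selection in the new data, so its accuracy estimate is not inflated by a search. This plan selects features by significance in the same subjects in which it then estimates accuracy. Leave-one-out does not remove that selection, because each left-out subject has already helped to choose the features.

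Two things are at stake. First, the protocol expects the work to yield a reliable means of diagnosis, and an accuracy figure obtained this way could look good with no signal at all. Second, if the search returns features other than the pilot's two, a reader cannot tell whether the pilot result failed or was merely displaced.

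**Working it through.** **The plan's own figure.** The documents give no power, effect size or expected accuracy for EVestG in TBI, so there is nothing to reproduce.

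**Inputs**
- Subjects: 20 patients and 20 controls (Study Population/Participants).
- Stimuli: 7 (Objective 4). Segments: 6, three outward and three on return; ears: 2 (EVestG Measurement).
- Scalar feature types: 5, namely mean, variance, fractal dimension, kurtosis and skewness (Data analysis).
- Threshold: p below 0.05, with no multiplicity adjustment stated (Data analysis).

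**Candidate counts (assumed, since the plan gives no total)**
- 7 × 6 = 42
- 42 × 2 = 84
- 84 × 5 = 420

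**Step 1: false positives in the search.** With k independent features and no true difference, P(at least one p below 0.05) = 1 − 0.95^k.
- k = 42: 0.88
- k = 84: 0.99
- k = 420: about 1.00, with 420 × 0.05 = 21 false positives expected

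Correlated features would lower the probabilities of at least one false positive.

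**Step 2: leave-one-out accuracy after selection.** Pure-noise simulation, 20 v 20, 400 runs, linear discriminant analysis. The best two of k features are picked on all 40 subjects before leave-one-out, as a stand-in for the plan's selection at p below 0.05.

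| k | Mean accuracy | Runs with 27/40 or more correct |
|---|---|---|
| 42 | 68% | 59% |
| 84 | 70% | 79% |
| 420 | 75% | 97% |

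With two features fixed beforehand and only the discriminant refitted, mean accuracy is about 50%, and 27/40 is reached in about 2% to 5% of runs. A fully locked rule reaches it in about 2%. Repeating the selection inside each leave-one-out fold also returns mean accuracy to about 50%.

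**Step 3: what a locked rule could show on the 40 baseline recordings.** Under chance, X ~ Binomial(40, 0.5).
- P(X ≥ 26) = 0.040 and P(X ≥ 27) = 0.019, so 27 is the smallest count with one-sided p at or below 0.025.

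True accuracy is an assumption. Under an equal-variance normal model, the best accuracy at Mahalanobis distance D is Φ(D/2).
- D = 1.0: Φ(0.50) = 69%, P(X ≥ 27) = 0.66
- D = 1.2: Φ(0.60) = 73%, P(X ≥ 27) = 0.82
- D = 1.35: Φ(0.675) = 75%, P(X ≥ 27) = 0.90

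**Step 4: precision.** Exact 95% intervals:
- 34/40 correct: 70% to 94%
- 17/20 for sensitivity: 62% to 97%

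**The case against.** **Exploration is legitimate here.** The protocol calls the study a pilot, and searching for features is a proper use of one. This stands, and it is why the search should stay, labelled as exploratory. It does not excuse an accuracy estimate that exceeds chance on noise.

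**The two features may be tested anyway.** A reader might infer that the pilot features are discarded and that every EVestG result will be a new discovery. The documents do not support that. The features may lie within the searched set, and the plan also brings in a decision algorithm, whose inputs it does not describe, and a check against clinical diagnoses. What is missing is a pre-specified test: none of these steps is described as a locked test of the two pilot features.

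**The pilot may not have fixed a rule.** A reader might take the two features to have been named in advance. The caption gives only their number and kind, and the documents mention no cut-off, stimulus or segment for that pilot. This stands, so the fix must be conditional.

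**It would not be a clean replication.** The pilot concerned mild TBI, while this trial sets no severity limit and requires persistent symptoms. A failure could reflect case mix. Nor do the documents say whether pilot participants may enrol. Both points stand and should be stated.

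**The features need not respond to rTMS.** A reader might go further and make the two features the lead Treatment v Sham comparison. Nothing in the documents shows that features separating injured from healthy people change with stimulation. Power gives no support either. At 10 v 10 with an assumed difference of 1.2 SD, each feature has 72% power at the plan's 0.05, against 60% at 0.025.

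**Power contrasts can be tilted.** At 20 v 20 and D = 1.0, a Hotelling test has 78% power on two features, against 41% when they sit among 10 and 11% among 30. These figures assume that all the signal lies in the pilot's two. If they carry half of D², their power is 47%. The point should not rest on this contrast.

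**Conclusion.** The concern holds in a limited form. The plan cites a two-feature separation as its evidence in mild TBI, does not pre-specify a test of it in the new subjects, and relies on an accuracy estimate that averages about 68% to 75% on pure noise for 42 to 420 candidates. Those figures assume independent features, selection of the best two, and counts built from the recording design; the actual inflation depends on how many features are computed and how correlated they are.

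The conclusion covers TBI v Control at baseline only. It does not bear on whether EVestG tracks response to rTMS, and it does not show that the pilot result is wrong. It also rests on the caption of a figure that could not be seen.

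**What to change.** In the Data analysis section, before any EVestG analysis:

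1. Name the two pilot features of Figure 1.
2. If the pilot fixed a rule, or one can be locked from pilot data alone, apply it unchanged to the week-0 recordings of the 20 patients and 20 controls. Leave out anyone who was in the pilot. Report sensitivity and specificity with exact intervals as the pre-specified diagnostic result.
3. If no rule can be locked, pre-specify a two-feature comparison of TBI v Control at baseline instead.
4. Label the wider feature search as exploratory, including the Objective 5 search for treatment-related change. If it reports a leave-one-out accuracy, repeat the selection inside each fold.
5. State that the pilot was in mild TBI and that this trial sets no severity limit.

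The cost is a paragraph of text and, if no rule exists, some work on the pilot data; no new subjects or recordings are needed. Leaving out pilot participants would reduce the 40 and widen the intervals. The lead diagnostic figure may also look less favourable than a newly optimised one.

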## **Objectives**

The objectives of this proposal are sorted in three key themes as follows.

### Theme 1: Applying rTMS treatment and its evaluation by neuropsychological and clinical assessments

1. Recruit people (from Riverview Health Center and also from [name] referrals), who have had a head injury within the past two to 12 months, have a clear diagnosis of TBI, and have persistent post-TBI symptoms. Collect standard neuropsychological assessment data at baseline.

2. Enroll the study participants into a “Sham Group” and a “Treatment Group” with a three-week protocol, and apply the treatment.
3. Record spatio-temporal assessments before and after treatment sessions, and examine the efficacy of rTMS treatment on the post-TBI symptoms by standard clinical and neuropsychological assessments by statistical analysis.

Theme 2: Monitoring treatment efficacy by objective measures, EVestG and spatio-temporal assessments

4. Record EVestG data with all its seven current stimuli at baseline (before the treatment) and immediately after treatment and also four and eight weeks after the last treatment.
5. Analyze EVestG data for extracting the optimum measures (biofeatures) showing the changes due to rTMS treatment.
6. Optimize (reduce the number of stimuli if possible) the EVestG recording protocol upon the results of Objective 5.
7. Examine the statistical correlation of the EVestG biofeatures representing the TBI recovery with data from the clinical and neuropsychological assessments as well as spatio-temporal assessments (derived in Objective 3).

Theme 3: Evaluating the objective measures of EVestG and spatio-temporal assessments in Control group

8. Recruit 20 age-and-gender-matched individuals with no history of head injury and record their EVestG data four times with a similar schedule to that of TBI patients, and investigate the consistency of the EVestG data between the sessions and compare with those of people with TBI during treatment.
9. Run the spatio-temporal assessments at the same sessions of EVestG recording in the Control Group and examine the effect of learning on the performance in these assessments.

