### **Exclusion Criteria for all Participants**

- 1) Use of neuro- or psycho-active medications as published in recommendations [26]
- 2) Active use of illicit drugs
- 3) History of epilepsy
- 4) History of any other brain lesions including tumors, infectious, vascular, or metabolic lesions
- 5) Severe or recent heart diseases
- 6) Alcoholism
- 7) Pregnancy
- 8) The presence of metallic objects in the body; dental implants are fine but people with pacemakers are to be excluded; anything that is unsafe under MRI would be considered unsafe for TMS [26].
- 9) Lack of ability to adequately communicate (understand, read, speak) in English and understand the experimental protocol.
- 10) Pending litigation (i.e., patients with pending actions regarding disability reports, litigation, or other kinds of financial compensation).

Participants will receive the details of the study, and be asked to sign a written consent form prior to experiments. Upon meeting the eligibility criteria and providing informed consent, each patient participant will be randomly assigned to either treatment or sham groups; this assignment will not be revealed to the patients until the end of study. *The Sham Group's participants will be offered a course of treatment after the study is finished if the results show improvement beyond the placebo for the participants in Treatment Group.* Patients will be thoroughly assessed by the medical collaborators for their symptoms, and localization of the damage to the brain. The cognitively healthy Control Group will not receive any rTMS treatment. All participants will complete a series of cognitive and mental assessments, and EVestG assessments. The Control Group will go through a lesser number of questionnaires as there is no need for run concussion severity assessment on control group. The details of the study procedure are described below, and Table 1 summarizes the study protocol.

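### EVestG features chosen because they change with rTMS cannot, in the same 20 patients, also be valid evidence that rTMS works

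*Combined protocol and SAP*

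**What the plan says.** The Proposal Summary gives EVestG an evaluative role: "The treatment efficacy and monitoring TBI patients' recovery will be objectively assessed using Electrovestibulography", alongside clinical assessments.

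Under Objectives, Theme 2, Objective 5 is to "Analyze EVestG data for extracting the optimum measures (biofeatures) showing the changes due to rTMS treatment". Objective 6 would reduce the number of stimuli on the strength of that result. Objective 7 is to "Examine the statistical correlation of the EVestG biofeatures representing the TBI recovery with data from the clinical and neuropsychological assessments", as well as with the spatio-temporal assessments.

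The Data analysis section compares extracted biofeatures between Sham and Treatment. It uses MANOVA to look for differences in any of them across sessions and groups, with a threshold of 0.05 for every test. Discriminant analysis with leave-one-out follows, on the features already found significant. The same section also says that features will be examined for those specific to concussion, so the selection rule is not stated in one consistent way.

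Study Population/Participants gives 10 patients per arm. The plan contains no list of features, no primary EVestG time point, no separate sample and no multiplicity adjustment.

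**The concern.** Objective 5 makes response to rTMS the reason for keeping a feature. If the same patients' data then supply the Treatment versus Sham test, the test is applied to the winners of a search on that very contrast. Some feature will appear to respond even if rTMS does nothing, and its apparent effect will be large because it was picked for being large. Randomisation, sham and blinding do not correct for this, and neither does leave-one-out run after selection.

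A second, smaller problem is one of labelling. If Objective 7's features are those that Objective 5 yields, a feature chosen because it moved under rTMS is described as representing recovery. Moving under treatment and recovering from injury are different properties, and the first does not establish the second.

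What is at stake is Theme 2: a reported EVestG response to rTMS, a shortened recording protocol, and a monitoring marker, any of which could be products of selection.

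**Working it through.** The plan gives no power or error-rate figure for EVestG, so there is nothing of its own to reproduce. The check asks how often the planned search finds something when nothing is there.

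**Inputs from the plan.** 10 versus 10 patients (Study Population/Participants); 7 stimuli (Objective 4); 2 ears and 6 segments per stimulus (EVestG Measurement); 3 statistics given as examples, or 5 with mean and variance (Data analysis); threshold 0.05, taken as two-sided.

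**Assumed.** The number of candidates, bracketed as:
- low: 7 × 3 = 21
- high: 7 × 2 × 6 × 5 = 420

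Each feature is counted once, as a single change score. The plan has three post-baseline recordings, so free choice of time point would add to these counts. Correlation between features is taken as 0 to 0.5.

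**Chance of at least one false feature.** For independent features it is 1 − 0.95^m:
- m = 21: 1 − 0.95^21 = 0.66
- m = 420: 1 − 0.95^420 ≈ 1.00

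For correlation 0.5, null simulations (two-sample t test on each feature, no true effect) give about 0.44 and 0.97. The expected number of false features is 0.05 × m, about 1 and 21.

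**Apparent size of the best null feature** (simulation): about 0.9 to 1.1 SD with 21 candidates, 1.4 to 1.7 SD with 420. The truth is 0.

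**Does leave-one-out protect?** With the top three features selected on all patients first, null accuracy is 0.64 to 0.71 (21 candidates) and 0.75 to 0.86 (420). With selection repeated inside each fold it is 0.48 to 0.49, which is chance.

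**Would the omnibus MANOVA protect?** Only with few features. Error degrees of freedom are 20 − 2 = 18 for two arms and 40 − 3 = 37 for three groups, so it cannot be fitted to hundreds of features at once.

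**Objective 7.** The best null feature was correlated with an unrelated clinical score. If the score does not differ by arm, about 5% of correlations are significant, so there is no inflation. If it differs by 1 SD, 11 to 12% are significant with 21 candidates and 20 to 25% with 420.

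**Does the fix work?** The feature with the largest week-0 TBI versus Control difference (20 versus 20) was selected and then tested once for Treatment versus Sham change, again under no effect. The false-positive rate was about 5%. Within-group movement towards controls on the same feature was falsely significant in 6 to 16% of runs against a nominal 2.5% (assumed test-retest reliability 0.5 to 0.8, 21 to 420 candidates). That is regression to the mean.

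**Power after the fix**, one fixed feature, 10 versus 10, normal approximation: 0.20, 0.43, 0.61 and 0.77 at assumed differences of 0.5, 0.8, 1.0 and 1.2 SD. The t distribution gives slightly less (0.40 at 0.8 SD).

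**The case against.** The trial is labelled a pilot, and developing a measure is a legitimate pilot aim. Objectives 5 and 6 read as development, and the Data analysis section's mention of concussion-specific features is close to the remedy proposed here. This stands as a reason to label the work exploratory. It does not rescue the arm comparison, because the Proposal Summary still presents EVestG as objective assessment of efficacy and nothing marks Objectives 5 to 7 as hypothesis-generating.

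The candidate counts are not in the plan, and the pre-movement segment may serve as a comparator rather than a separate outcome. Also true: 97 to 100% describes an assumption, not the plan. The low count still gives 44 to 66%.

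Three stronger readings are tempting, and the documents do not support them.
- *EVestG cannot serve as an objective measure at all.* The defect lies in inference from searched features in this sample, not in the recording.
- *The recovery marker is circular.* Objective 7 uses clinical scores as an outside anchor, its correlation is inflated only when those scores also differ by arm, and the text does not say outright that its features are those of Objective 5.
- *Stimulation shifts EVestG directly.* The Background says that "the vestibular nucleus is linked to the pre-frontal cortex path", and also "The cognitively healthy Control Group will not receive any rTMS treatment", so no group receives rTMS without TBI. But the anatomical link is cited to explain change after injury, and no rTMS effect on EVestG is reported. It is a possibility that the design does not exclude, not a finding.

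**Conclusion.** The concern holds for the EVestG comparison of Treatment with Sham. Run as written, the plan has between a substantial and a near-certain chance of a false EVestG efficacy signal: about 44 to 66% with 21 candidates, 97 to 100% with 420. These figures rest on assumed feature counts, on correlation between 0 and 0.5, and on feature-by-feature testing at 0.05.

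It does not follow that the trial's efficacy evidence fails as a whole. Objective 3 tests symptoms by clinical and neuropsychological assessments, independently of EVestG. Objective 7 needs a change of label and status rather than removal: response to rTMS alone is not grounds for calling a feature a marker of recovery.

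**What to change.** Reword Objective 5 and the Data analysis section as follows.

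1. Choose a short list of EVestG features and one time point without reference to rTMS response. Two sources exist: the week-0 TBI versus Control recordings, already scheduled in Table 1, or the earlier pilot (Figure 1: "Separation of mTBI and control subjects using two post potential features"). The text does not name the pilot features, so they would have to be written out, and they come from mild TBI, whereas this trial sets no severity limit.
2. Lock the list and time point before treatment codes are opened.
3. Test EVestG efficacy only as Treatment versus Sham change on that list, adjusting for multiplicity if more than one feature is kept.
4. Do not use within-group movement towards controls as evidence, because week-0 selection produces it through regression to the mean.
5. Report as exploratory, to be confirmed in new patients: features found by searching for rTMS response, the stimulus reduction in Objective 6 that rests on them, and the Objective 7 correlations. Show the correlations for Sham alone as well, descriptively; with n = 10, significance at 0.05 would need |r| of at least 0.63.

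The cost is wording only, with no new data. The downside is that a feature which responds to rTMS but does not separate TBI from controls at baseline can be reported only as exploratory. The honest test also has low power, about 0.43 at an assumed 0.8 SD, which argues for a very short list and for reporting estimates with confidence intervals.
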